## Tegaderm™ Placement for Bag Mask Ventilation in the Bearded Patient

abort or proceed with the protocol. In the event of a cardiac event or equivalent the protocol will be aborted and the patient will be excluded from the trial.

12.2. Study data will be derived from the research interaction with the patient, and the electronic medical record (EMR). These data will be recorded on a data collection form that will be deidentified and associated with a unique study code. Data to be collected are as follows.

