## 7. Study Endpoints

7.1. *Describe the primary and secondary study endpoints.*

Primary outcome: Mask leakage, defined as the difference between average inspired and expired tidal volumes, as a percentage of inspired volume. Patients will serve as their own controls; the comparison is of the difference in leakage in the Tegaderm™ versus baseline conditions.

Secondary outcomes: 1. Difference in airway resistance between Tegaderm™ and baseline conditions, 2. Difference in peak inspiratory pressure between Tegaderm™ and baseline conditions, 3. Extent to which mask leakage change with Tegaderm™ depends on beard length.

7.2. *Describe any primary or secondary safety endpoints.*

If bag/mask ventilation is difficult and a Tegaderm™ not already in place, one will be placed in an effort to provide a better seal for the mask. If ventilation continues to be difficult, an Attending Anesthesiologist would attempt bag mask ventilation, consider placing an oral airway, and follow the difficult airway algorithm (6) by using supraglottic airway as a rescue device if deemed necessary. This event will be considered data and included in analyses.

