Once standard ASA monitors are applied, an adult-sized oxygen mask (Medline™ Anesthesia Mask) will be placed over patient's face for pre-oxygenation with 100% O2 at a rate of 10 liters/minute until measured expired oxygen  $\geq 80\%$ . Immediately prior to administration of induction medications we will open the randomization envelope denoting which technique we will apply first. General anesthesia will be induced with 1–3 mcg/kg bolus of fentanyl, 1.5 mg/kg of lidocaine, 2–3 mg/kg propofol and 0.6–1mg/kg Rocuronium for ideal mask ventilation conditions. The study interval will be specified as the period beginning with apnea, anesthesia induction with neuromuscular

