### **14. Provisions to Monitor the Data to Ensure the Safety of Subjects**

*This section is required when research involves more than Minimal Risk to subjects. Describe:*

- 14.1. The PI will perform data and safety monitoring every 2 months, but the PI works closely with all study team members and will be kept apprised of study progress, including any adverse events.
- 14.2. The PI will review the collected data and the Electronic Anesthesia Record which already includes relevant safety outcomes and patient participant EMR. Relevant data includes oxygenation and ventilation parameters, airway pressures, and other information relevant to airway management. The data will be reviewed for desaturation events, elevated airway pressures, and any other adverse clinical outcomes related to airway management during the study. Any such adverse events would be immediately apparent in the stated records. The PI will obtain statistical advice as appropriate, but adverse events are expected to be sufficiently uncommon that they are likely to be addressed on a case-by-case basis.
- 14.3. The PI will refer to the EMR as appropriate to obtain relevant context on any adverse events.
- 14.4. Mask ventilations are routine prior to intubation and safety profiles are well established. It is not anticipated that the medical literature will report new findings that call the safety of this study into question.
- 14.5. The PI will review the incidence of adverse events related to Tegaderm™ use in this study to determine whether they exceed the incidence that would be expected without the use of the intervention. If, in the PI's opinion, adverse events occur and are related to the study, the PI will suspend the study and notify HRRC as noted in 14.6 below.
- 14.6. In accordance with HRRC policy, the PI will suspend the study in the event of any adverse outcome that is both significant and likely due to the procedure under investigation, in the PI's opinion, and report the event to HRRC for its review and subsequent recommendation.
- 14.7. The PI will notify HRRC in the event of study termination under 14.6 above.

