## **16. Data Management/Confidentiality**

- 16.1. Most members of the research team are physicians who interact with these and similarly-situated patients on a daily basis.
- 16.2. The research does require the use of direct identifiers (e.g. MRN) in order to accurately obtain complication data and link it to procedural data.
- 16.3. The research requires the use of Private Health Information (PHI), but the investigators will not disclose any identifiable information except as required by law.
- 16.4. The data do not include information that is typically considered to be sensitive, such as HIV status, substance abuse, or criminal behavior.
- 16.5. The investigators do not plan to pursue a Certificate of Confidentiality.
- 16.6. All investigators have completed routine UNM Health Sciences Center (HSC) training on the secure management and use of patient data. Identifiable data on paper forms will be maintained in a locked cabinet in a study team member's Anesthesiology Department office, which is a patient-restricted area; and in electronic format will be stored on HSC secure servers, which are password-protected.
- 16.7. Data will be deidentified upon completion of data collection and entry into a spreadsheet stored on UNM HSC secure servers, but will be identifiable (via a linking document containing study ID numbers and MRNs) until that point in order to permit accurate linkage of procedural and outcome data.

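### Section 12.1 excludes a patient who has a cardiac event after the order is assigned, and nothing says that patient will still be counted in the reported results

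*Combined protocol and SAP*

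**What the plan says.** The rule closes the procedural description in section 12.1: "In the event of a cardiac event or equivalent the protocol will be aborted and the patient will be excluded from the trial". The triggering event is not defined further, and no cause is specified.

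Four other parts of the protocol bear on it.

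- **Assignment (12.1).** "Immediately prior to administration of induction medications we will open the randomization envelope denoting which technique we will apply first". The order is therefore fixed and known before the study interval begins.
- **Difficult ventilation (7.2).** After describing difficult ventilation and its rescue, the protocol says: "This event will be considered data and included in analyses".
- **Safety monitoring (section 14).** Under 14.2, "The PI will review the collected data and the Electronic Anesthesia Record which already includes relevant safety outcomes and patient participant EMR", and "The data will be reviewed for desaturation events, elevated airway pressures, and any other adverse clinical outcomes related to airway management during the study". Under 14.5, "The PI will review the incidence of adverse events related to Tegaderm™ use in this study" and compares it with what would be expected without the intervention. Under 14.6, "the PI will suspend the study in the event of any adverse outcome that is both significant and likely due to the procedure under investigation"; that judgement belongs to the PI, and the event is then reported to HRRC. Section 16.2 keeps identifiers "in order to accurately obtain complication data and link it to procedural data".
- **Withdrawal (section 15).** 15.1 foresees no likely withdrawal without consent, apart from a patient who cannot follow instructions before induction. 15.2 says that a patient who withdraws after surgery is not analysed but is still reported as having entered the study.

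The analysis plan in 13.1 is a paired within-patient comparison. It names no analysis set and gives no rule for an aborted procedure.

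**The concern.** The sentence in 12.1 joins two separate decisions. Stopping study procedures is a clinical matter. Removing the patient from the trial is a data matter, and here it is triggered by an adverse outcome that arises after assignment. Exclusions of that kind are normally avoided because they make the reported group look healthier than the group that was treated.

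Two features add to the difficulty. The extension to equivalent events has no definition, so someone must judge whether it applies. The staff making that judgement know whether the dressing is on the face.

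At stake is the accounting for harm. The stated aim in 2.3 is to inform guidelines on managing these airways. A report of no serious events would mislead if patients with such events had been removed from the count.

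**Working it through.** **Inputs.** The pilot has 25 patients and initial authorization covers up to 50 (5.2, 5.3). The protocol gives no cardiac-event rate, alpha, power or dropout figure, so there is no figure of its own to reproduce on this point. Most of the check is a comparison of sections.

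**Step 1: timing.** The envelope is opened just before the induction drugs. The study interval starts with apnea and runs to the end of the mask-ventilation minutes. Any event in that interval follows assignment, so the exclusion is post-assignment and outcome-dependent.

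**Step 2: 12.1 against 7.2.** 7.2 concerns difficult ventilation and its rescue. 12.1 concerns a cardiac or equivalent event. They apply to different patients unless difficult ventilation progresses to a cardiac event. In that case 7.2 keeps the patient's event as data and 12.1 removes the patient. No text says which prevails.

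**Step 3: 12.1 against section 15.** 15.1 lists no such exclusion. 15.2 promises that a voluntary post-surgery withdrawal is still reported as an entry. There is no matching promise for the 12.1 exclusion, so a change of mind is better accounted for than a serious event.

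**Step 4: 12.1 against section 14.** The review in 14.2 uses the anesthesia record and the medical record, and nothing restricts it to patients kept in the trial. Under 14.6 a significant event judged likely due to the procedure suspends the study and goes to HRRC. Monitoring therefore survives the exclusion. Two points stay open:

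- 14.5 speaks of incidence but defines no denominator and does not say whether excluded patients count.
- The test in 14.6 is relatedness to the procedure under investigation. An event in the no-alteration period may not meet it, although it is information about the comparator.

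**Step 5: data capture.** The study-information list in 12.2.2 has provider level, paralytic, beard length, randomization result and respiratory parameters. It has no item for an adverse event or for the condition in use when one occurs.

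**Step 6: illustration, assuming exactly one event.** The intervals are exact (Clopper-Pearson) 95% limits. For 0/n the upper limit is 1 − 0.025^(1/n). For 1/n the lower limit is 1 − 0.975^(1/n), and the upper limit is the 0.975 quantile of Beta(2, n − 1).

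| Enrolled | Patient kept | Patient excluded |
|---|---|---|
| 25 | 1/25 = 4.0% (0.1% to 20.4%) | 0/24 = 0% (upper limit 1 − 0.025^(1/24) = 14.2%) |
| 50 | 1/50 = 2.0% (0.05% to 10.6%) | 0/49 = 0% (upper limit 1 − 0.025^(1/49) = 7.3%) |

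**Step 7: how often the rule might be used.** The chance of at least one event is 1 − (1 − p)^n, over assumed rates p.

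| Assumed p | n = 25 | n = 50 |
|---|---|---|
| 0.1% | 2.5% | 4.9% |
| 0.5% | 11.8% | 22.2% |
| 1% | 22.2% | 39.5% |
| 2% | 39.7% | 63.6% |

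These rates are assumptions chosen to show a range. None comes from the protocol.

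**The case against.** The strongest reply is that section 14 already deals with the matter. The PI reviews clinical records that exist whether or not the patient is analysed, and identifiers are kept so that complications can be linked. The operative trigger in 14.5 and 14.6 is the occurrence of a related event, not a rate. One cardiac event judged significant and related suspends the study whatever the denominator. This stands. A reader might infer from 12.1 that the event vanishes from the safety record, and the documents do not support that.

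A reader might also infer that the rule hides the most serious airway-related harm. That goes too far as well. The sentence names no cause and follows the text on hemodynamic instability, while failed seal and rescue are in a separate paragraph. Patients with active or unstable cardiac disease, or with ASA status 4 or above, are not enrolled (4.3). An airway cause is possible but is not stated.

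Third, the loss to the efficacy analysis may be nil. A patient stopped before both 60-second periods are complete has no paired difference, excluded or not. This also stands, and it limits the remedy: breaths recorded before the event cannot simply be fed into the planned paired test.

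These replies do not reach the reported results. Section 14 governs oversight during the study. It does not say that a patient excluded under 12.1 will appear in the participant flow or in the published safety summary.

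**Conclusion.** The concern holds as a matter of accounting and reporting. 12.1 contains an explicit outcome-dependent exclusion after assignment, with an undefined trigger applied by staff who know the condition in use. It conflicts with 7.2 where failed ventilation leads to such an event, and it is absent from section 15. Read literally, it takes the patient out of the trial's reported results and leaves the denominator in 14.5 unclear. It does not take the event out of safety monitoring.

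The size cannot be computed from the documents. The 1/25 versus 0/24 comparison rests on an assumed single event and on the assumption that the reported safety count follows the exclusion. The effect on the leakage estimate is expected to be small. The point is worth correcting because the change is cheap and would prevent a false report of no events.

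**What to change.** Leave the decision to stop study procedures exactly as written. In 12.1, delete the clause that excludes the patient from the trial, and replace it with a statement on these lines: the patient remains in the participant flow and in the reported safety summary, with the assigned order and the condition in use at the time of the event.

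In 13.1, add that the patient enters the paired analysis if both periods were completed. Otherwise the patient is counted as an incomplete crossover, by order and condition, and any leakage already recorded is reported descriptively only.

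Then reconcile the related sections:

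- **7.2:** say that events kept as data include those that progress to the event named in 12.1.
- **12.2.2:** add an item for adverse events and the condition in use.
- **14.5:** state that the incidence counts all such patients in both numerator and denominator.
- **Section 15:** refer to stopped procedures and confirm that entry into the study is still reported.

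The cost is a few sentences and one or two lines on the data form. No patients, study procedures or clinical rules are added.

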12.2.1. Patient background information

- 12.2.1.1. Past medical history
- 12.2.1.2. Surgery Type
- 12.2.1.3. Race
- 12.2.1.4. Obstructive Sleep Apnea History
- 12.2.1.5. Mallampati score
- 12.2.1.6. Age
- 12.2.1.7. Weight
- 12.2.1.8. Height
- 12.2.1.9. Body Mass Index

12.2.2. Study information

- 12.2.2.1. Level of the provider
- 12.2.2.2. Paralytic
- 12.2.2.3. Beard length (perioral)
- 12.2.2.4. Randomization result
- 12.2.2.5. Respiratory parameters

## 13. Data Analysis

13.1. *Describe the data analysis plan, including any statistical procedures.*

Paired data (within patient differences in leakage,  $PP_{ins}$ , and airway resistance) will be assessed with paired t-test or Wilcoxon rank-sum test, depending on distribution normality. Beard condition groups will be compared on the primary outcome (leakage difference  $> 15\%$  significant) with ANOVA or Kruskal-Wallis test, also depending on distribution normality. Sensitivity analysis will provide percentage of observed standard deviation for detection of leakage difference and a traditional power analysis to provide the sample size required to detect significant outcome with our intervention.

13.2. *Provide a power analysis, if applicable*

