### 3. Study Design

- 3.1. Our study design is a randomized prospective crossover trial in adult patients (>18 years), with circumferential perioral facial hair longer than 5 mm who will undergo elective non-cardiac surgery in the main adult operating rooms of the University of New Mexico Hospital.
- 3.2. Allocation concealment: Providers and subjects will be blinded to which method they will start with (control versus intervention) via envelope method prior to induction of general anesthesia.
- 3.3. Subjects who are consented to participate in the study will have facial hair measured as a continuous variable length (mm).
- 3.4. Mask ventilation operators will be confined to anesthesiology residents, anesthesiologist assistants (AA), and AA students all of whom are familiar with bag mask ventilation. Mask ventilation will occur using a two-handed Thenar-Eminence (TE) grip without the addition of an oropharyngeal airway. All operators will be instructed on how to perform this technique prior to patient enrollment. We will use Pressure Control ventilation mode on Anesthesia Ventilator machine (Dräger Perseus A500) set at 10 breaths per minute, I:E time of 1:2 and peak inspiratory pressure of 20 cm H2O, all of which are routine in our practice and within typical ranges at the national level. These are specified only in order to reduce practice variation not related to the intervention itself. An external pneumotachograph device and sensors (Phillips Respironics NM3™ respiratory profile monitor; Respironics CAPNOSTAT® Mainstream CO2 sensor) will be used to measure ventilation parameters ( Vtins; mL, VtExp; mL, PPins; cm H2O, Res; cm H2O/L/sec) with collected data electronically saved to a dedicated flash drive associated with the pneumotachograph .

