## Tegaderm™ Placement for Bag Mask Ventilation in the Bearded Patient

blockade to completion of one minute of mask ventilation with and without Tegaderm™ use. Patients will act as their own controls. Anesthesia induction and apnea will be defined as no voluntary respiratory effort and the absence of the eyelid reflex. Complete Neuromuscular blockade will be defined as Train of Four Ratio of **0/4** with neuromuscular monitoring at the *Corrugator Supercilii* muscle.

Once subjects are apneic and induced, **3** mask ventilation breaths will be administered in order to ‘acclimate’ the user to the mask and insure a proper thenar-eminence (TE) grip is being used. The randomized crossover trial will be started once complete neuromuscular blockade is verified. Every consecutive trial will alternate between starting with Tegaderm™ use and no alteration with patients acting as their own controls. Both no alteration and Tegaderm™ portion of exam will use the Resironics NM3™ (Resironics Deutschland, Herrsching, Germany) and CAPNOSTAT® 5 (Phillips Healthcare corporation, Eindhoven, The Netherlands) sensors to measure primary outcomes: Inspired tidal volumes (  $V_{t_{ins}}$ ; ml ), expired Tidal Volumes of End Tidal CO2 (  $V_{t_{Exp}}$ ; ml ) which will be used to determine predefined adequate BMV (Inspired Tidal Volume- Expired Tidal Volume difference of <15% defined as adequate) and secondary outcomes: within-patient differences between Tegaderm™ and no-alteration conditions for peak inspiratory pressures (  $PP_{ins}$ ; cm H2O ) and airway resistance (  $Res$ ; cm H2O/l/sec ) for 60 seconds, and facial hair grouping comparisons. The anesthesia machine will be set to deliver standardized pressure-controlled ventilation using common parameters: peak inspiratory pressure of 20 cm H2O, 10 breaths per minute, and an inspiratory-expiratory ratio of 1:2. These values are within common ranges used in standard practice, but may be modified during surgery as determined to be clinically appropriate by the attending anesthesiologist. General anesthesia will be maintained with sevoflurane 4-6% with 100% O2 at a rate of 6 liters per minute. Once data is gathered for the first part of the trial (no alteration or Tegaderm™), we will change our technique and collect data for second 60 seconds component of the trial in similar fashion to initial data collection.

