## Tegaderm™ Placement for Bag Mask Ventilation in the Bearded Patient

The data and statistics that would be required for a formal sample-size calculation with a reliable power estimate are not available. For that reason, the investigators plan a 2-phase process. In the first (external pilot) phase, the investigators plan to enroll 25 participants following a published guideline (Whitehead AL, et al. *Statistical Methods in Medical Research* 2016; 25:1057-73) and use the generated data to obtain effect-size and standard deviation information. Those statistics will permit a valid sample size calculation for the second phase, i.e. the main trial. The investigators will submit a modification to HRRC with sample size justification for the main trial prior to enrolling any patients for it.

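### The non-parametric fallback in section 13.1 is the Wilcoxon rank-sum test, which is for independent samples; the paired crossover data call for the signed-rank test

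*Combined protocol and SAP*

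**What the plan says.** Section 13.1 describes its input as "Paired data (within patient differences in leakage", peak inspiratory pressure and airway resistance), and says these "will be assessed with paired t-test or Wilcoxon rank-sum test, depending on distribution normality".

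The rest of the protocol agrees that the comparison is paired:

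- Section 3.1: "Our study design is a randomized prospective crossover trial in adult patients".
- Section 7.1, primary outcome: "Mask leakage, defined as the difference between average inspired and expired tidal volumes, as a percentage of inspired volume". It continues: "Patients will serve as their own controls; the comparison is of the difference in leakage in the Tegaderm™ versus baseline conditions".
- Section 12.1, secondary outcomes: "within-patient differences between Tegaderm™ and no-alteration conditions for peak inspiratory pressures" and for airway resistance.

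The signed-rank test is named nowhere. Section 13.1 does not mention sequence, period or order of conditions. The main-phase sample size has not been set; section 13.2 says: "The investigators will submit a modification to HRRC with sample size justification for the main trial".

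**The concern.** The rank-sum (Mann-Whitney) test needs two independent samples. A column of within-patient differences is one sample, so the fallback cannot be applied to the data that the same sentence describes. The rank test that corresponds to a paired t-test is the signed-rank test.

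The sentence governs the primary outcome and two of the three secondary outcomes. If normality is rejected, the analyst has to depart from the wording or guess what it means. One way to follow the name literally is to enter the Tegaderm and no-alteration values as two separate groups. That ignores the pairing, so the error rate is no longer the nominal one and, with positive within-patient correlation, the efficiency of the crossover is lost. Correcting the name silently at that stage would be an unplanned change made after the data had been examined.

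**Working it through.** **There is no figure to reproduce.** The documents state no alpha, power, effect size, SD, within-patient correlation or normality test. The 25 pilot patients come from a cited guideline. Only n = 25 below is the protocol's; every other input is an assumption.

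**Step 1: why the correlation matters.** Let each measurement have SD σ, and let ρ be the correlation between a patient's two values. The mean difference has variance 2σ²(1 − ρ)/n. An analysis that treats the conditions as independent uses 2σ²/n. Its standard error is therefore wrong by a factor of √(1 − ρ), and the true two-sided error is roughly 2[1 − Φ(1.96/√(1 − ρ))]. This is the large-sample result for means, given for orientation:

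- ρ = −0.3: 1.96/1.140 = 1.72, error 8.6%
- ρ = 0: 1.96/1 = 1.96, error 5.0%
- ρ = 0.3: 1.96/0.837 = 2.34, error 1.9%
- ρ = 0.5: 1.96/0.707 = 2.77, error 0.6%
- ρ = 0.7: 1.96/0.548 = 3.58, error 0.03%

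**Step 2: rank-sum itself, run on the two conditions in every trial.** Simulation of 25 normal pairs, two-sided 5%, 100,000 trials per correlation. The effect is 0.584 SD of the differences. The paired t-test then has noncentrality 0.584 × √25 = 2.92 on 24 degrees of freedom, which is 80% power.

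| ρ | Rank-sum type I error | Rank-sum power |
|---|---|---|
| −0.3 | 8.0% | 86% |
| 0 | 4.7% | 79% |
| 0.3 | 2.0% | 66% |
| 0.5 | 0.7% | 50% |
| 0.7 | 0.1% | 24% |

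Signed-rank on the same data has type I error of 4.7–4.8% and power of 78% throughout. These figures describe misuse in every trial, not the plan's loss.

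**Step 3: the plan as a whole.** The fallback is used only when normality is rejected. Assume Shapiro-Wilk at 5% on the differences, with 30,000 trials per scenario. Two data models were used: normal, and a leakage bounded between 0 and 100% (logit-normal, mean logit −0.85, SD 1.5, mean baseline leak about 35%, ρ set on the logit scale). In the bounded model the shift was set so that signed-rank has about 80% power. The net change in power is approximately

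(share of trials using the fallback) × (rank-sum power − signed-rank power in those trials).

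Signed-rank power in the bounded-model fallback trials was 83–84%, taken as 83.5% in the product:

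| ρ | Share using fallback | Rank-sum power there | Product, points | Simulated net change, points |
|---|---|---|---|---|
| −0.3 | 6% | 90% | +0.4 | +0.4 |
| 0 | 8% | 86% | +0.2 | +0.2 |
| 0.3 | 11% | 75% | −0.9 | −1.0 |
| 0.5 | 14% | 57% | −3.7 | −3.6 |
| 0.7 | 18% | 30% | −9.6 | −9.7 |

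For normal data the fallback is used in about 5% of trials, and the net changes over the same correlations are +0.4, 0.0, −0.7, −1.5 and −2.8 points. The simulation standard error of the net changes is 0.04–0.17 points.

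**Step 4: type I error of the whole plan.** It stays at 4.4–5.4% in every scenario. Naming rank-sum instead of signed-rank raises it by at most 0.1 point and lowers it by at most 0.8 point.

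**Step 5: is there a reading under which rank-sum is right?** Yes. Comparing period differences between the two sequence groups is a valid crossover test. With groups of 12 and 13, normal data and a shift of 0.5 SD of a single measurement, its type I error was 4.2–4.6%. Its power was 63% against 65% for signed-rank at ρ = 0.5, and 84% against 86% at ρ = 0.7. The starting order is recorded (section 12.2.2). But section 13.1 mentions neither sequence nor period, and it sets rank-sum beside a paired t-test on within-patient differences. It does not describe this analysis.

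**The case against.** The strongest reply is that this is a naming slip that the sentence itself exposes. It calls the data paired and offers a paired t-test, and an analyst holding one column of differences would find that rank-sum cannot be run. To reach the harmful analysis, someone would have to disregard the description of the data. The size is also soft. The power figures use the pilot n of 25, although the efficacy test matters most in the main phase, whose size is unknown. The largest loss comes from the highest correlation in one assumed model. Nothing in the documents suggests the negative correlation that would make the test anti-conservative. Finally, the analyst has a third route, the sequence-group test, which is valid.

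Most of this stands as a limit on the consequence. A slip is the likely explanation, the harm is conditional, and the figures are illustrations. It does not make the text right. Section 13.1 is the only place where the test for the primary outcome is named, nothing elsewhere corrects it, and leakage as a bounded percentage could well be skewed enough to trigger the fallback. That three different analyses could be run under the present wording is itself a reason to settle it in advance.

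**Conclusion.** The point holds. The fallback test for the primary outcome and for two of the secondary outcomes is wrong as written; the paired t-test is right. No figure in the documents changes.

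The consequence is modest and arises only when normality is rejected and the test is run on the two conditions as if they were independent. On the assumptions above, the whole plan loses about 1 point of power or less at correlations up to 0.3, 1.5 to 3.6 points at 0.5, and 2.8 to 9.7 points at 0.7, depending on the data model. Overall type I error remains close to 5%. These sizes rest on assumed values for correlation, alpha, normality test, data model and effect, so no particular loss is established for this trial. The error should be fixed because it sits in the primary analysis and costs almost nothing to correct.

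**What to change.** In section 13.1, replace the Wilcoxon rank-sum test with the Wilcoxon signed-rank test on the within-patient difference. When the pilot data are used to size the main phase, base the calculation on the same paired analysis; no calculation exists yet, so this is a matter of consistency and not a correction. A Hodges-Lehmann estimate with a 95% confidence interval would be a useful but optional addition to reporting.

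The cost is one line of analysis wording. Data collection and conduct do not change, and the correction can go into the sample-size modification that the investigators already plan to submit.
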